0.0 Study Summary

Title	Phase II Study of Nivolumab and Ipilimumab in Mucinous Colorectal and Appendiceal Tumors
Short Title	Nivo/Ipi In Mucinous CRC
IRB Number	831705
Protocol Number	UPCC 28218
Phase	Phase II
Methodology	Single Arm Phase II
Study Duration	18-24 months accrual plus 6 months follow-up
Study Center(s)	Abramson Cancer Center at University of Pennsylvania
Objectives	
Primary Objective
 
 1. To estimate six-month progression-free survival by iRECIST 
Secondary Objectives
 
 1. To determine overall response rate, duration of response, and progression-free survival by iRECIST and RECIST 1.1. To determine overall survival. 2. To estimate the toxicity rates by CTCAE v 5.0. 
Exploratory Objectives
 
 1. To measure T-cell subsets and markers of T-cell function in peripheral blood as a potential biomarker of response 2. To define the immune effects in pre- and post-treatment biopsy specimens with analysis of tumor-infiltrating lymphocytes, including immune subsets, mutational load, and TCR sequencing 3. To correlate imaging response with quantitative changes in cell-free tumor DNA, extracellular vesicles, and/or other circulating tumor materials

Number of Subjects	21
Diagnosis and Main Inclusion/Exclusion Criteria	
Inclusion Criteria:
 
 1. Colorectal or appendiceal mucinous tumor with peritoneal-only metastatic disease 2. Microsatellite stable by PCR and/or mismatch repair proficient by immunohistochemistry 3. ECOG PS 0-1 4. Standard laboratory parameters 5. Prior therapy with a fluoropyrimidine, oxaliplatin, and irinotecan unless contraindicated or refused. Prior treatment with antiangiogenic and/or anti-EGFR antibody therapy is permitted but not required 
Exclusion Criteria:
 
 1. Significant autoimmune disease 2. Bowel obstruction within the past 60 days 3. Use of systemic steroids other than for adrenal hormone replacement
Study Products, Dose, Route, Regimen	
Product: Nivolumab Dose: 480mg Route: IV Regimen: Every 4 weeks
 
Product: Ipilimumab Dose: 1mg/kg Route: IV Regimen: Every 8 weeks

Duration of administration	Subjects will continue on study therapy until disease progression, unacceptable toxicity, withdrawal of consent, or 24 months of therapy.

Statistical Methodology	
For patients with colorectal adenocarcinoma who have progressed on standard chemotherapy, treatment with either TAS-102 or regorafenib in chemotherapy-refractory patients results in median PFS of approximately 2 months and 6-month PFS of approximately 17%. With 21 evaluable subjects, we will have 81% power to reject a 6-month PFS of 17% (H_0) versus 40%, assuming exponential survivorship and using a two-sided binomial alpha = 0.10.
 
Toxicity rates will be calculated by category with 95% confidence intervals. We will also utilize a Bayesian toxicity monitoring plan, and estimate the posterior probability that the rate of treatment discontinuation due to toxicity exceeds 30%. ORR, PFS and DOR will be assessed by both RECIST v. 1.1 and iRECIST and calculated with 90% confidence intervals. Kaplan Meier methods will be used to estimate the survival curves for PFS and OS. Median PFS, OS, and DOR will be calculated with 90% confidence intervals. If progression is confirmed by imaging (iCPD) or clinically (iUPD without follow-up imaging), the date of initial progression on imaging (iUPD) will be used.

-------------------------	--

Table of Contents

0.0	Study Summary.....	2
1.0	Objectives	6
2.0	Background.....	6
3.0	Study Design	8
4.0	Study Population	9
5.0	Treatment Plan.....	11
6.0	Dosing Delays/Dose Modifications.....	12
7.0	Study Procedures.....	12
8.0	Study Treatment Details.....	13
9.0	Statistical Plan	17
10.0	Safety and Adverse Events	19
11.0	Data Handling and Record Keeping.....	26
12.0	Study Monitoring, Auditing, and Inspecting.....	27
13.0	Ethical Considerations	27
14.0	Study Finances.....	28
15.0	Publication Plan.....	28
16.0	References.....	28
17.0	Schedule of Events	30
	Appendix A: Definition of Non-Childbearing Potential and Medically Acceptable Methods of Birth Control	32
	Appendix B: Management Algorithms for Nivolumab and Ipilimumab	33
	Appendix C: RECIST 1.1 Criteria	41
	Appendix D: Immune-Related Response in Measurable Lesions (iRECIST).....	43

1.0 Objectives

1.1 Primary Objective

To determine six-month progression-free survival by iRECIST

1.2 Secondary Objectives

1. To determine overall response rate, duration of response, and progression-free survival by iRECIST and RECIST 1.1. To determine overall survival.
2. To determine the toxicity rates by CTCAE v 5.0

1.3 Exploratory Objectives

1. To measure T-cell subsets and markers of T-cell function in peripheral blood as a potential biomarker of response
2. To define the immune effects in pre- and post-treatment biopsy specimens with analysis of tumor-infiltrating lymphocytes, including immune subsets, mutational load, and TCR sequencing
3. To correlate imaging response with quantitative changes in cell-free tumor DNA, extracellular vesicles, and/or other circulating tumor materials

2.0 Background

2.1 Mucinous Colorectal and Appendiceal Adenocarcinoma

Mucinous histology is found in about 15% of colorectal adenocarcinoma, and a higher proportion of appendiceal adenocarcinomas, and connotes a poor prognosis in the metastatic setting, with shorter progression-free and overall survival and decreased responsiveness to chemotherapy [1,2]. Despite this unfavorable phenotype, a highly select subset of patients with peritoneal-only disease can achieve long-term disease control with aggressive surgical management using cytoreductive surgery (CRS) in combination with heated intraperitoneal chemotherapy (HIPEC) [3]. *We hypothesize that the mechanism through which HIPEC results in long-term disease control is not direct cytotoxicity but rather immune activation against mucinous tumor antigens.* This immune activation has been demonstrated in a “HIPEC-vaccine” murine model, with subsequent immune rejection of distant tumor injections after HIPEC [4].

The mutational landscape of mucinous adenocarcinomas is poorly-described, as samples are frequently paucicellular, but increasing data shows that they are genetically distinct from non-mucinous colorectal cancers [5, 6]. More importantly, mucinous tumors have increased expression of extracellular proteins such as modified mucins that can be highly immunogenic [7]. Only recently have sequencing tools been developed to characterize the immunogenicity of these carbohydrate antigens [8], although a variety of vaccine and engineered T-cell studies have shown these mucins to be targetable by the immune system [9, 10]. In ovarian tumors, immunopeptidomic profiling found that MUC16 was by far the most immunogenic of more than 1,100 tumor-specific antigens, eliciting a T-cell response in 80% of healthy blood donors [11]. Recently, PD-1 has also been shown to play a major role in

suppressing immunity against Tn and other tumor-associated carbohydrate antigens [12]. No study has yet been conducted to evaluate checkpoint blockade in this specific subset of colorectal cancer. This will be a phase II study to determine the efficacy of combination checkpoint blockade nivolumab and ipilimumab in peritoneal-only mucinous colorectal and appendiceal adenocarcinoma.

2.2 Nivolumab Mechanism of Action

PD-1 is a member of the CD28 family of T-cell co-stimulatory receptors that also includes CD28, CTLA 4, ICOS, and BTLA. PD-1 signaling has been shown to inhibit CD-28-mediated upregulation of IL-2, IL-10, IL-13, interferon- γ (IFN- γ) and Bcl-xL. PD-1 expression also been noted to inhibit T cell activation, and expansion of previously activated cells. Evidence for a negative regulatory role of PD-1 comes from studies of PD-1 deficient mice, which develop a variety of autoimmune phenotypes. These results suggest that PD-1 blockade has the potential to activate anti-self T-cell responses, but these responses are variable and dependent upon various host genetic factors. Thus, PD-1 deficiency or inhibition is not accompanied by a universal loss of tolerance to self-antigens.

In vitro, nivolumab (BMS-936558) binds to PD-1 with high affinity (EC50 0.39-2.62 nM), and inhibits the binding of PD-1 to its ligands PD-L1 and PD-L2 (IC50 \pm 1 nM). Nivolumab binds specifically to PD-1 and not to related members of the CD28 family such as CD28, ICOS, CTLA-4 and BTLA. Blockade of the PD-1 pathway by nivolumab results in a reproducible enhancement of both proliferation and IFN- γ release in the mixed lymphocyte reaction (MLR). In vivo blockade of PD-1 by a murine analog of nivolumab enhances the anti-tumor immune response and result in tumor rejection in several immunocompetent mouse tumor models (MC38, SA1/N, and PAN02). Clinical efficacy has been demonstrated in a variety of tumor types, and it is currently FDA approved for the treatment of melanoma, non-small cell lung cancer, Hodgkin's lymphoma, renal cell carcinoma, squamous cell carcinoma of the head and neck, urothelial carcinoma, microsatellite instability-high tumors, and hepatocellular carcinoma.

2.3 Ipilimumab Mechanism of Action

CTLA-4, an activation-induced T-cell surface molecule, is a member of the CD28:B7 immunoglobulin superfamily that competes with CD28 for B7. CTLA-4 mediated signals are inhibitory and turn off T cell-dependent immune responses. Ipilimumab is a fully human monoclonal IgG1 κ that binds to the CTLA-4 antigen expressed on a subset of T cells from human and nonhuman primates. The proposed mechanism of action for ipilimumab is interference of the interaction of CTLA-4 with B7 molecules on APCs, with subsequent blockade of the inhibitory modulation of T-cell activation promoted by the CTLA 4/B7 interaction. It is currently FDA approved for the treatment of melanoma.

2.4 Rationale for Adding Ipilimumab to Nivolumab

Preclinical and clinical evidence suggests synergy between nivolumab and ipilimumab, which target distinct mechanisms to limit T cell activation, PD-1 and CTLA-4 respectively. In vitro combinations of nivolumab plus ipilimumab increase IFN- γ production 2- to 7-fold over either agent alone in a mixed lymphocyte reaction. In a murine melanoma vaccine model, blockade with either CTLA-4 or PD-1 antibodies increased the proportion of CTLA-4 and PD-1-expressing CD4/CD8 tumor infiltrating T effector cells, and dual blockade increased tumor infiltration of T effector cells and decreased intratumoral T regulatory cells, as compared to either agent alone. The combination of nivolumab and ipilimumab has been shown to be more effective than either agent in monotherapy

in the treatment of a variety of tumors including melanoma, lung, renal cell carcinoma, and MSI-high colorectal cancer.

2.5 Safety of Nivolumab and Ipilimumab

The combination of nivolumab and ipilimumab has the potential for increased frequencies of AEs compared to ipilimumab monotherapy or nivolumab monotherapy. The toxicity profile of the nivolumab + ipilimumab combination has been shown to correlate with the ipilimumab dose: with increasing doses of ipilimumab, there has been an increase in frequency of AEs and, potentially, the severity of these events; however, no novel toxicities have been demonstrated versus either agent alone. In the current regimen for this protocol, the dose of ipilimumab will be cumulatively lower than the approved dose level for the combination for the treatment of advanced and metastatic melanoma. The toxicity profile with lower doses of ipilimumab has been established to be very similar to that of nivolumab monotherapy as detailed below in section 2.6.

The most common (reported at > 10% incidence) treatment related AEs with the combination are fatigue, rash, pruritus, diarrhea, lipase increased, pyrexia, ALT increase, AST increased, amylase increased and vitiligo. These classes of AEs are expected for the combination of nivolumab and ipilimumab based on the known AE profile of each drug alone. In addition, many of the Grade 3-4 AEs are laboratory in nature (ie, LFTs, lipase, amylase), occur without clinical sequelae, and are been manageable and reversible following intervention dose delays or with systemic steroid treatment. However, immune AEs have the potential to be fatal if not detected early and managed per the established algorithm, and fatal AEs have been reported for both ipilimumab and nivolumab monotherapy. Adverse drug reactions with fatal outcome in clinical trial participants treated with nivolumab monotherapy and nivolumab and ipilimumab combination therapy are listed in the current version of the nivolumab investigator brochure (IB).

A pattern of immune-related AEs has been defined, for which management algorithms have been developed; these are provided in Appendix B. Most high-grade events are manageable with the use of corticosteroids or hormone replacement therapy (endocrinopathies) as instructed in these algorithms.

[figure not shown]
2.6 Rationale for Dose Selections

The nivolumab doses of 480 mg Q4W was selected for this study based on clinical pharmacokinetic data and modeling showing similar drug exposure and no change in safety compared to dosing every 2 weeks using either weight-based (3mg/kg) or flat dose (240mg) regimens [13]. In the CA209012 study in non-small cell lung cancer, ipilimumab 1 mg/kg using Q6W and Q12W schedules were assessed and were found to be safe in combination with nivolumab 3 mg/kg Q2W. Both the Q6W and Q12W arms were associated with improved and manageable tolerability compared to the arms with more frequent ipilimumab dosing (Q3W). Both arms also had encouraging efficacy in all participants and enhanced benefit in participants with PD-L1 expression, with Q6W arm having numerically higher median PFS compared to the Q12W arm. There were some imbalances observed between the Q6W and Q12W arms, as follows. With both schedules showing a similar safety and efficacy profile, a Q8W schedule was chosen to align with nivolumab dosing and maintain expected safety and efficacy.

3.0 Study Design

This is a single-arm phase II study of twenty-one subjects with mucinous adenocarcinoma of the colon, rectum, or appendix with prior systemic therapy with a fluoropyrimidine, oxaliplatin, and irinotecan. Treatment will consist

of nivolumab 480mg every 4 weeks and ipilimumab 1mg/kg every 8 weeks until disease progression, unacceptable toxicity, or 2 years of therapy. Imaging assessments will be conducted every 8 weeks (+/-2 weeks). If progression is noted on imaging in the setting of clinical stability, subjects may remain on study and have confirmatory imaging in 4-8 weeks per iRECIST criteria.

4.0 Study Population

4.1 Inclusion Criteria

1. Subjects must have signed and dated an IRB-approved written informed consent form prior to the performance of any protocol-related procedures that are not part of standard care.
2. Colorectal or appendiceal mucinous adenocarcinoma with peritoneal-only metastatic disease. It is recognized that in some patients, peritoneal disease will predominate without distinction of the site of origin, and such patients will be eligible.
3. Microsatellite stable by PCR and/or mismatch repair proficient by immunohistochemistry
4. ECOG performance status of 0 or 1
5. Prior therapy with a fluoropyrimidine, oxaliplatin, and irinotecan unless contraindicated or refused. Prior treatment with antiangiogenic and/or anti-EGFR antibody therapy is permitted but not required
6. Measurable disease by RECIST v. 1.1
7. Laboratory parameters (within 14 days prior to the start of treatment):
 - a. Absolute neutrophil count \geq 1500/ μ L
 - b. Platelets \geq 100,000/ μ L
 - c. Hemoglobin \geq 9.0 g/dL
 - d. PT/INR or PTT \leq 1.5xULN
 - e. Creatinine \leq 1.5xULN OR creatinine clearance \geq 50 mL/min by Cockcroft-Gault formula
 - f. Total bilirubin \leq 1.5xULN
 - i. Subjects with Gilbert's Syndrome must have a total bilirubin level of \leq 3.0xULN
 - g. Albumin \geq 3.0 g/dL
 - h. AST and/or ALT: \leq 3.0xULN
8. Subjects with HIV are permitted provided they meet the following criteria:
 - a. CD4+ cell count \geq 250 cells/mm³
 - b. No history of AIDS-defining conditions other than low CD4+ count
 - c. If subject is on antiretroviral therapy, there must not be expected significant drug-drug interactions with study treatment

4.2 Exclusion Criteria

1. Bowel obstruction within the past 60 days

Version: 11/24/2020

CONFIDENTIAL

This material is the property of the University of Pennsylvania

2. Subjects who are currently pregnant, planning to become pregnant, or breast-feeding.
 - a. *Females participants of child-bearing potential are required to use an effective contraception method (see Appendix A) or abstain from intercourse during treatment and for at least 5 months following the last dose*
 - b. *Males participants with partners of child-bearing potential are required to use an effective contraception method (see Appendix A) or abstain from intercourse during treatment and for at least 7 months following the last dose*
3. Subjects who, in the opinion of the physician, would not be clinically appropriate for receipt of the therapy regimen associated with participation
4. Subjects with contraindications to immune checkpoint therapy, as follows:
 - a. Interstitial lung disease that is symptomatic or may interfere with the detection and management of suspected drug-related pulmonary toxicity
 - b. Prior organ allograft or allogeneic bone marrow transplantation
 - c. Pre-existing thyroid abnormality with thyroid function that cannot be maintained in the normal range with medication
 - d. Active autoimmune disease, except for vitiligo, type 1 diabetes mellitus, asthma, atopic dermatitis, or endocrinopathies manageable by hormone replacement; other autoimmune conditions may be allowable at the discretion of the principal investigator
 - e. Condition requiring systemic treatment with corticosteroids
 - Systemic steroids at physiologic doses (equivalent to dose of oral prednisone 10 mg) are permitted.
 - Intranasal, inhaled, topical, intra-articular, and ocular corticosteroids with minimal systemic absorption are permitted.
5. Established non-peritoneal metastatic disease, including but not limited to metastases to the liver, lung, brain, extra-abdominal lymph nodes, and bone
6. A second primary malignancy that, in the judgment of the investigator, may affect interpretation of results
7. Prior treatment with an anti-PD-1, anti-PD-L1, or anti-CTLA-4 antibody
8. Toxicities attributed to prior anti-cancer therapy other than alopecia, fatigue, and peripheral neuropathy must have resolved to Grade 1 or baseline before administration of study drug. In addition, a washout period will be required for prior therapies as specified:
 - a. No chemotherapy within 14 days prior to first dose
 - b. No investigational product(s) (IPs) and/or biologic therapy within 28 days or 5 half-lives, whichever is longer, prior to first dose
 - c. No major surgery within 28 days prior to first dose. Any surgery-related AE(s) must have resolved at least 14 days prior to first dose.
 - d. No radiation therapy with curative intent within 28 days prior to first dose. Prior focal palliative radiotherapy must have been completed at least 14 days prior to first dose.
9. Active hepatitis B or hepatitis C, defined as the following:
 - a. Hepatitis B surface antigen positive or HBV DNA PCR >100 IU/mL
 - b. Hepatitis C antibody positive unless HCV RNA PCR is negative (i.e. undetectable viral load)
10. Prisoners or participants who are involuntarily incarcerated. (Note: under specific circumstances a person who has been imprisoned may be included as a participant. Strict conditions apply and BMS approval is required.)
11. Participants who are compulsorily detained for treatment of either a psychiatric or physical (eg, infectious disease) illness

4.3 Withdrawal, Removal, Evaluability and Replacement of Subjects

Subjects may withdraw from the study at any time at their own request in which case investigators will seek permission from such subjects for investigators to continue to contact them every 6 months for follow-up; however, subjects may choose to withdraw completely from all procedures and follow-up. Subjects may also be withdrawn at any time at the discretion of the Investigator for safety, behavioral, or administrative reasons. If a subject does not return for a scheduled visit, every effort should be made to contact the subject. In any circumstance, every effort should be made to document the subject outcome, if possible. The Investigator should inquire about the reason for withdrawal, and request the subject to return for a final visit and follow-up regarding any unresolved AEs. If the subject withdraws from the study and also withdraws consent for disclosure of future information, no further evaluations should be performed and no additional data should be collected. The Sponsor may retain and continue to use any data collected before such withdrawal of consent.

An individual subject will not receive any further study drug if any of the following occur in the subject in question:

- Progressive Disease by iRECIST (See Appendix C)
- Complete Withdrawal of consent from the study (no further data collection permitted)
- Withdrawal of consent from further treatment with study drug (data collection as per study schedule permitted)
- Lost to Follow up
- An AE that, in the opinion of the Investigator or the Sponsor, contraindicates further dosing including but not limited to hypersensitivity to any of the therapeutic agents
- Pregnancy or intent to become pregnant
- Subject Non-Compliance that, in the opinion of the investigator warrants withdrawal (e.g., refusal to adhere to the scheduled visits)
- Initiation of another anti-cancer therapy (excluding surgery or palliative radiotherapy), including another investigational agent

4.3.1 Evaluability and Replacement of subjects

Subjects will be evaluable for toxicity if they receive at least one dose of either nivolumab or ipilimumab. Subjects will be evaluable for efficacy if they receive at least one dose of nivolumab and one dose of ipilimumab and undergo repeat imaging at least 4 weeks and no more than 12 weeks after initiating therapy on study. Subjects who do not meet the criteria for evaluability for efficacy will be replaced.

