5.0 Treatment Plan

Treatment will consist of nivolumab 480mg every 4 weeks and ipilimumab 1mg/kg every 8 weeks. Imaging assessments will be conducted every 8 weeks (+/- 2 weeks) for the first 24 weeks then every 8-12 weeks (+/- 2 weeks). If progression is noted on imaging in the setting of clinical stability, subjects may remain on study and have confirmatory imaging in 4-8 weeks per iRECIST criteria (see Appendix C)

Table 1: Treatment Plan

Version: 11/24/2020

CONFIDENTIAL

This material is the property of the University of Pennsylvania

Agent	Dose	Route	Frequency (within a 56-day cycle)
Nivolumab	480mg	IV infusion per institutional guidelines and the Package Insert	Days 1, 29
Ipilimumab	1mg/kg	IV infusion per institutional guidelines and the Package Insert	Day 1

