9.0 Statistical Plan

9.1 Endpoints

9.1.1 Primary Endpoint: Progression-Free Survival at 6 Months

Progression-free survival at 6 months (PFS6) is defined as the proportion of patients free from disease progression by iRECIST criteria (see Appendix D) or death at the time of week 24 restaging imaging (within acceptable 2 week window). Subjects who withdraw from the study prior to week 24 imaging will be considered to have progressed unless imaging is obtained at or after 24 weeks (within acceptable 2-week window), no progression is observed, and the subject has not initiated any other anti-cancer therapy prior to 6-month imaging. The final efficacy analysis will not be performed until all subjects have experienced progression or death, initiated additional anti-cancer therapy prior to 6 months from the start of study therapy (which will be considered progression), been lost to follow-up, or undergone at least six months of follow-up.

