9.1.2.5 Safety Analysis

Safety analysis will be performed on the safety – evaluable population, defined as all enrolled subjects who received at least one dose of study treatment. Summaries of AEs, SAEs, deaths, changes in laboratory test results, vital signs and exposure to study drug will be presented. Drug exposure will be summarized to include treatment duration, number of doses and dose intensity. Laboratory data with values outside reference ranges will be summarized by NCI-CTCAE v 5.0 grades.

We will conduct a Bayesian toxicity monitoring plan every 3 patients with a target discontinuation rate due to toxicity of 30%. We assume a *Beta*(1,2) prior, equivalent to one discontinuation of treatment (both ipilimumab and nivolumab) due to toxicity in 3 treated patients. Early study termination for toxicity will be considered based on a posterior probability that the rate of treatment discontinuation due to toxicity exceeds 30%. Early termination will be considered if treatment discontinuation due to toxicity occurs in 2 of 3 patients (0.84 posterior probability), 3 of 6 patients (0.81), 4 of 9 patients (0.79), 5 of 12 patients (0.78), or 6 of 15 patients (0.78).

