9.2 Sample Size Determination and Methods

For patients with colorectal adenocarcinoma who have progressed on standard chemotherapy, treatment with either TAS-102 or regorafenib in chemotherapy-refractory patients results in median PFS of approximately 2 months and 6-month PFS of approximately 17%. In phase III trials of nivolumab in chemotherapy-refractory solid tumors (e.g. non-small cell lung cancer [15], urothelial carcinoma [16]) six-month PFS of 30-40% have correlated with an overall survival benefit, as many patients without progression by 6 months will have durable benefit. We therefore would find a 6-month progression-free-survival of 40% to be highly promising in this study population. With 21 evaluable subjects, we will have 81% power to reject a 6-month PFS of 17% (H0) versus 40%, assuming exponential survivorship and using a two sided binomial test with alpha = 0.10.

The primary endpoint of 6-month PFS will be assessed using iRECIST criteria to account for potential pseudoprogression (See Appendix D). If progression is confirmed by imaging (iCPD) or clinically (iUPD without

follow-up imaging), the date of initial progression on imaging (iUPD) will be used. ORR, PFS and DOR will be assessed by both RECIST v. 1.1 and iRECIST and calculated with 90% confidence intervals. PFS at 6 months will be estimated as a crude rate with a 90% CI. Kaplan Meier methods will be used to estimate the survival curves for PFS and OS. ORR will be summarized as a binomial proportion. Median PFS, OS, and DOR will be calculated with 90% confidence intervals.

Analysis of T-cell function, TCR sequencing, and circulating tumor materials will be an exploratory and hypothesis-generating analysis of potential biomarkers. Immune assays in tissue and blood will seek to demonstrate immune activation, generate potential biomarkers to predict response and identify responding T-cell populations and their respective target(s). Circulating tumor measurements will seek to improve upon measurability of response and generate potential genomic biomarkers of response. Logistic regression will be used to evaluate any association of response status and PFS6 with marker, and markers will be summarized by response status and PFS6. Cox regression will be used to test any association between a time-to-event outcome (PFS, OS) and marker expression. Other analyses will be descriptive.

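### The plan does not say whether replaced treated subjects stay in the PFS6 denominator; if they leave, early failures drop out and the primary estimate is probably biased upward

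*Combined protocol and SAP*

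**What the plan says.** Four parts of the combined protocol and SAP bear on who is counted in PFS6.

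- **Section 4.3.1** makes a subject evaluable for efficacy after "at least one dose of nivolumab and one dose of ipilimumab and undergo repeat imaging at least 4 weeks and no more than 12 weeks" from the start of therapy. It then says: "Subjects who do not meet the criteria for evaluability for efficacy will be replaced". Death or clinical progression before a scan is not exempted.
- **Section 9.1.1** defines PFS6 as the proportion of patients "free from disease progression by iRECIST criteria (see Appendix D) or death at the time of week 24 restaging imaging". It adds: "Subjects who withdraw from the study prior to week 24 imaging will be considered to have progressed", except where a progression-free scan is obtained at or after week 24 and no other anti-cancer therapy was started before it. On timing it says: "The final efficacy analysis will not be performed until all subjects have experienced progression or death", or have met one of the other listed conditions.
- **Section 9.2** says: "With 21 evaluable subjects, we will have 81% power to reject a 6-month PFS of 17% (H0) versus 40" percent. It calls PFS6 a crude rate with a 90% CI and does not name the population.
- **Section 9.1.2.5** defines the only analysis population in section 9, the safety set: "all enrolled subjects who received at least one dose of study treatment".

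**The concern.** A treated subject who dies in week 5 without a scan is a PFS6 failure under 9.1.1 and a non-evaluable, replaced subject under 4.3.1. No sentence says which rule sets the primary denominator. Efficacy evaluability is defined only in 4.3.1, so 4.3.1 and 9.2 read together imply that this subject leaves and another takes the place. The primary set would then depend on what happens after treatment starts.

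PFS6 is the primary endpoint of a single-arm trial tested against a fixed 17%, and there is no control arm in which the same selection could cancel out. Two analysts could each follow the protocol and report different primary results.

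The likely direction is upward. Both drugs are due on day 1. Section 5.0 says: "Imaging assessments will be conducted every 8 weeks (+/- 2 weeks) for the first 24 weeks", so the first scan falls in weeks 6 to 10, inside the 4-to-12-week window. A subject who is progression-free and on study would usually qualify. One who dies or deteriorates with no scan in that window cannot.

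**Working it through.** **Inputs.** From 9.2: n = 21, null 17%, alternative 40%, two-sided binomial test at 0.10, stated power 81%. Two further inputs are assumptions, because the documents give neither: the share f of treated subjects lost to non-evaluability, and the share g of those lost who are progression-free at week 24.

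**The plan's own power.** The normal approximation without continuity correction is

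Φ{[(0.40 − 0.17)√21 − 1.645√(0.17 × 0.83)] / √(0.40 × 0.60)} = 0.813,

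which matches 81%. The exact binomial with success at 7 or more of 21 gives power 0.800 and an upper tail of 0.0526 at 17%. A boundary of 8 or more gives power 0.650. The stated power is not in dispute, and 7 or more is the boundary consistent with it.

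**Effect on the rate and on false positives.** If the true all-treated PFS6 is 17% and lost subjects leave,

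evaluable rate = (0.17 − f·g) / (1 − f).

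With g = 0 (every lost subject a failure, so these are upper bounds for each f):

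| f | Evaluable PFS6 | P(7 or more of 21) |
|---|---|---|
| 0 | 17.0% | 5.3% |
| 5% | 0.17/0.95 = 17.9% | 6.7% |
| 10% | 0.17/0.90 = 18.9% | 8.5% |
| 15% | 0.17/0.85 = 20.0% | 10.9% |
| 20% | 0.17/0.80 = 21.3% | 13.9% |

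**When the direction changes.** The bias is upward for g below 17%, zero at g = 17% and downward above it. At f = 10%:

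- g = 10%: rate (0.17 − 0.010)/0.90 = 17.8%, P(7 or more of 21) = 6.5%
- g = 25%: rate (0.17 − 0.025)/0.90 = 16.1%, P(7 or more of 21) = 4.1%

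**Effect on a single result.** The two-sided exact p below sums all outcomes no more likely than the one observed. Start at 7/21 and add back dropped failures:

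| Count | Rate | p | Rejects at 0.10 |
|---|---|---|---|
| 7/21 | 33.3% | 0.073 | yes |
| 7/22 | 31.8% | 0.083 | yes |
| 7/23 | 30.4% | 0.096 | yes |
| 7/24 | 29.2% | 0.167 | no |

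Three dropped failures reverse a result at the boundary. With doubled-tail p-values, 7/21 gives 0.105 and does not reject. The boundary is then 8/21 (p = 0.035), and five dropped failures are needed to reverse it (8/25 p = 0.099; 8/26 p = 0.123).

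**How often three losses would occur.** The number of losses before 21 evaluable subjects are reached is negative binomial with success probability 1 − f. The chance of three or more is 11%, 41%, 69% and 87% for f = 5%, 10%, 15% and 20%. These are chances of losses, not of a reversed result.

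**The case against.** The section that defines the endpoint leans towards inclusion. Section 9.1.1 speaks of patients, not evaluable patients. It scores withdrawal as failure with no minimum time on study and holds the analysis until all subjects have an outcome. Its withdrawal rule would have no effect on those who leave before a first scan if 4.3.1 had already removed them. Replacement may mean only that subjects are added. On that reading there is no bias. This stands as a fair reading, but it does not settle the matter: the all-subjects sentence governs timing, and retaining replaced subjects takes n above the 21 on which 9.2 bases the test.

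The size is assumed throughout. Entry requires ECOG 0–1, albumin of at least 3.0 g/dL and no bowel obstruction in the past 60 days, which argues against a loss of 15–20% without excluding it. Subjects who had both drugs and a scan in weeks 4–12 stay evaluable even if they later die or withdraw. Progression-free subjects lost for a missed or off-window scan, or for single-drug dosing, pull the other way. All of this stands. At f = 5%, about one loss, the effect is small.

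The reversal example needs exactly 7/21 as well as three losses. At a true 17% with g = 0, P(exactly 7/21) is 4.3%, 5.3%, 6.5% and 8.0% for the four values of f. Multiplying by the chance of three or more losses gives about 0.5%, 2.2%, 4.5% and 7.0%. By the same two-sided test, 8/21 would need six dropped failures (8/26 p = 0.069; 8/27 p = 0.117). The example shows sensitivity at the boundary and does not describe a frequent event.

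Finally, an evaluable primary set with clear rules and an all-treated sensitivity analysis would also remove the ambiguity. It would not remove the selection on events after treatment starts.

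**Conclusion.** The concern holds and should be fixed. That the primary denominator is unresolved is clear from the text: applying the evaluability rule would drop failures that 9.1.1 counts. Upward bias is probable, conditional on replaced subjects leaving and on fewer than 17% of them being progression-free at week 24. The size rests on an assumed early-loss share and a true PFS6 of 17%. For f between 5% and 20%, with every loss a failure, the rate is inflated by about 1 to 4 percentage points. The chance of crossing the 7-of-21 boundary rises from 5.3% to between 6.7% and 13.9%.

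**What to change.** - In 4.3.1 and 9.1.1, define the primary PFS6 set as all subjects who receive at least one dose of study drug, the set 9.1.2.5 already uses for safety. The both-drugs and scan criteria then no longer apply to the primary set.
- Score these subjects by the existing 9.1.1 rules, and state that death or clinical progression before a first scan is a failure.
- State that any treated subject who is replaced stays in the denominator.
- Report the 4.3.1 evaluable set as a sensitivity analysis.
- In 9.2, state which set the 17%, 40% and 81% refer to. Name the two-sided binomial convention too, since it fixes the rejection boundary at whatever n is reached.

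**Cost.** Wording in three sections, and possibly a slightly lower PFS6 estimate. If 40% was meant for all treated patients, 21 treated subjects keep 80.0% exact power and none are added. If it was meant for evaluable patients, the all-treated target becomes 40% × (1 − f) and power must be restated:

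| f | All-treated target | Power, 21 treated, 7 or more | Power with replaced subjects kept in |
|---|---|---|---|
| 5% | 38% | 74% | 79% (n = 22, 7 or more) |
| 10% | 36% | 68% | 78% (n = 23, 7 or more) |
| 15% | 34% | 61% | 66% (n = 25, 8 or more) |
| 20% | 32% | 53% | 63% (n = 26, 8 or more) |

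The n in the last column is 21/(1 − f), rounded, with the two-sided exact boundary for that n.
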